5.6.1.2. Severity Criteria

All AEs and laboratory data will be coded for severity using a modified version of the FDA grading table, based on the version of September 2007 (US DHHS FDA CBER 2007), included in Section 6.6.

For AEs not identified in the grading table, the guidelines in the clinical protocol will be applied.

The severity of solicited signs and symptoms will be graded in the reactogenicity diary by the participant based on the severity assessment provided in the reactogenicity diary and then verified by the investigator using the Toxicity Grading Scale. Severity of the measured events will be

derived from the diameter [for erythema and swelling] and the temperature measurements [for fever].

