5.6.2. Laboratory, Vital Signs, and Physical Examinations

Hematology, Chemistry and Urinalysis tests will be performed locally within 72 hours of blood sample collection, according to the Schedules of Activities (CTP 1.3), at Screening (optional, at the discretion of the investigator), at Day 1 (pre-dose): Day 8, Day 15, Day 29 and at delivery (postpartum 1) and postpartum 43 (42 days after delivery). For further details on all laboratory assessments refer to CTP 8.2.3.

Continuous laboratory variables will be summarized using the following statistics, as appropriate: number of observations, arithmetic mean (mean), standard deviation (SD), standard error (SE), median, minimum, and maximum. Frequencies and percentages (one decimal place) will be generated for categorical laboratory variables. Denominator for the percentages is the number of participants in the considered population and phase for a certain regimen (incidence per 100 participants/phase).

For all adult participants, weight and height (and BMI) at baseline will be summarized using descriptive statistics. Physical exam will be summarized and listed for adults. Neonatal physical and birth exam will be summarized and listed for neonates.

Vital signs for adults and neonate/infants including temperature, pulse/heart rate, respiratory rate, blood pressure (adult participants only: systolic and diastolic) and blood oxygen saturation will be summarized over time, using descriptive statistics. Abnormalities emerging after vaccination will be tabulated by worst abnormality grade using the FDA table in Section 6.6.

Temperature will be measured at each scheduled time point and summarized using descriptive statistics. A listing of participants with fever will be provided for adults and neonates. Other vital signs abnormalities will be listed with corresponding grade.

For adult COVID-19 cases, temperature will be summarized over time for the duration of followup of COVID-19 episodes, using descriptive statistics.

All parent(s)/caregiver(s) of neonates/infants with (suspected) COVID-19 should measure blood oxygen saturation and body temperature.

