An abnormality (toxicity grade or abnormality based on normal ranges) will be considered as emerging in a particular period if it is worse than the baseline value. If the baseline is missing, the abnormality is always considered emerging. A shift from 'abnormally low' at baseline to 'abnormally high' post baseline (or vice versa) is also emerging. In case a laboratory test result is censored (no numeric value is available, but only a verbatim term) then a numeric value will be imputed by a value exceeding the cut-off value with one unit. (<x: subtract 1 unit from x, >x: add 1 unit to x: e.g., <3.45 is imputed with 3.44, <90 with 89 and >101 with 102).

In case no toxicity grades are defined for a test, the abnormalities (above/below normal range) will be used. In determining toxicity grades, the following rules are applied:

- worst grades/abnormalities are determined over the whole observational period for each trial period separately, including all post-baseline measurements of that period.
- The abnormalities 'abnormally low' and 'abnormally high' are considered equally important, i.e. if a participant has as well an abnormally low as an abnormally high value post-baseline, both abnormalities are shown in the tables. (This means that the sum of the percentages can be more than 100%).
- Note: as the grading scale for some parameters in the grading table has some gaps (zones where no toxicity grade definition exists), results falling in these zones will be allocated to the adjacent worst-case grade. For example if a laboratory result falls within the 'grey area' between the ranges for 'Grade 1' and 'Grade 2' in the FDA table, then this result would be allocated to 'Grade 2' (the adjacent worst-case grade).
- If a value falls within the grading as specified in the grading FDA table but using the local laboratory it falls within normal limits, the value is considered as normal. For example, if the local lab classifies a result as 'normal' within their prespecified limits, then the value can indeed be considered normal even when according to the FDA table it would be 'Grade 1'.

For the grades, no distinction will be made between test results of samples obtained under fasting and under non-fasting conditions.

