Protein	Trace	1+	2+	Hospitalization or dialysis
Glucose	Trace	1+	2+	Hospitalization for hyperglycemia
Blood (microscopic) – red blood cells per high power field (rbc/hpf)	1 - 10	11-50	> 50 and/or gross blood	Hospitalization or packed red blood cells (PRBC) transfusion

* The laboratory values provided in the tables serve as guidelines and are dependent upon institutional normal parameters. Institutional normal reference ranges should be provided to demonstrate that they are appropriate.

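### Read literally, the SAP's gap rule codes urine protein or glucose above 2+ as Grade 4 without the clinical event that defines Grade 4; at best the grade is ambiguous between 3 and 4

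*SAP*

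**What the plan says.** Section 5.6.1.2 sets the scope: "All AEs and laboratory data will be coded for severity using a modified version of the FDA grading table", and that table is in Appendix 6 (Section 6.6). Section 5.6.2 schedules the tests ("Hematology, Chemistry and Urinalysis tests will be performed locally within 72 hours of blood sample collection") at Day 1, 8, 15 and 29, at delivery and at postpartum Day 43, with screening optional. It takes the worst grade separately for each trial period. Section 5.1 adds that unscheduled results also count towards the worst grade.

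Section 5.6.2 recognises that the table has zones without a grade, and states that "results falling in these zones will be allocated to the adjacent worst-case grade". Its one example is a value between the Grade 1 and Grade 2 ranges: "then this result would be allocated to 'Grade 2' (the adjacent worst-case grade".

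The urine table in Appendix 6 grades protein and glucose identically up to Grade 3: trace, 1+, 2+. Grade 4 is "Hospitalization or dialysis" for protein and "Hospitalization for hyperglycemia" for glucose. The third urine row, blood, has an open upper end at Grade 3: "> 50 and/or gross blood".

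**The concern.** The gap rule suits small holes between adjacent numeric ranges. For ALT, for example, Grade 1 ends at 2.5 times the upper limit of normal and Grade 2 begins at 2.6, so a value of 2.55 goes to Grade 2 and nothing is distorted. Urine protein and glucose differ. Grade 3 is a single value, nothing is defined above it, and the next grade is an event and not a measurement. If the rule is applied there, a urine reading alone produces a Grade 4 entry.

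The study tests no hypothesis (Section 2), so its descriptive tables are its output. Pre-eclampsia and gestational diabetes are among the pregnancy-related events named in Section 5.4.1, so readers are likely to look at urine protein and glucose. A Grade 4 count that mixes hospitalised women with women who only had a high reading could not be interpreted from that table.

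**Working it through.** No figure in the SAP is at issue and there is no sample-size or error-rate calculation to reproduce. The check applies the Section 5.6.2 rule to the Appendix 6 urine rows.

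**Step 1. Grade each possible reading when no hospitalization or dialysis is recorded.** The narrow reading confines the gap rule to holes between two value ranges.

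| Urine protein or glucose | Defined in Appendix 6 | Literal gap rule | Narrow reading |
|---|---|---|---|
| negative | none | none | none |
| trace | Grade 1 | 1 | 1 |
| 1+ | Grade 2 | 2 | 2 |
| 2+ | Grade 3 | 3 | 3 |
| 3+ | no definition | 4 | 3 |
| 4+ | no definition | 4 | 3 |

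The two readings of the rule differ only above 2+.

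**Step 2. See how far the problem extends.** Fifteen rows or sub-rows of Appendix 6 with a Grade 4 defined only by an event were checked for whether Grade 3 is open-ended.

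- Open-ended, so no gap (13): tachycardia (>130), bradycardia (<45), systolic hypertension (>155), diastolic hypertension (>100), systolic hypotension (<80), respiratory rate (>25), fasting glucose (>125), random glucose (>200), BUN (>31), eosinophils (>5000), urine blood (>50 or gross blood), erythema (>100 mm), swelling (>100 mm).
- Closed at a single value (2): urine protein and urine glucose, both 2+.

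13 + 2 = 15, so the gap below an event-only Grade 4 is confined to these two rows.

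**Step 3. Look for a rule that overrides this.**

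- The local-range exception in Section 5.6.2 applies "if the local lab classifies a result as 'normal' within their prespecified limits". It reaches a reading above 2+ only if the laboratory calls that reading normal.
- The footnote that table values are guidelines offers no other allocation.
- The serum-table footnote moves a Grade 3 sodium value to Grade 4 only when a new seizure accompanies it. There the table asks for the event; the literal gap rule for urine does without it.
- No section has a separate rule for urine, or for Grade 4 criteria that are events.

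**Step 4. What one entry weighs.** Safety is summarised by vaccination group (Section 5.1). At the minimum recruitment targets in Section 3, one woman is 1/40 = 2.5% of Group 1, 2 or 3 and 1/25 = 4.0% of Group 4. These are targets. Enrolment ceased as of protocol amendment 7 and the SAP does not give the numbers reached. The calculation shows the weight of a single entry and says nothing about how many there will be.

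**The case against.** The best answer is that the rule does not apply here. It speaks of gaps, and its only example lies between two value ranges. A 3+ reading lies beyond the last value range, and an event has no place on the urine scale, so Grade 3 is the nearest grade defined by a value. This is a fair reading, and it is why one cannot say that the rule certainly produces Grade 4. But the SAP does not limit the rule in this way: it covers zones with no grade definition and directs results upwards. The objection turns a wrong allocation into an undetermined one, and the text still needs a sentence.

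A second answer concerns importance, and most of it stands. No primary endpoint is a laboratory grade. Section 5.6.2 also calls for frequencies of categorical laboratory variables, where the urine categories should be visible as reported. The Data Presentation Specifications could settle the coding, although the SAP does not say that they do.

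A reader might infer that true Grade 4 cases would be hidden. The documents do not support that. Section 5.6.1.3 tabulates SAEs over the whole study and pregnancy-related AEs separately, and provides listings or narratives for SAEs. Appendix 8 includes gestational diabetes, pre-eclampsia and eclampsia. Only the laboratory grade table itself would fail to separate the two kinds of entry.

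**Conclusion.** The point holds as a wording defect of limited reach. Read literally, Section 5.6.2 and the urine table together code protein or glucose above 2+ as Grade 4 without the defining event; read generously, they leave the grade open between 3 and 4. Two urine rows in the descriptive worst-grade laboratory tables are affected. No error rate, power or primary endpoint is touched.

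The conclusion assumes that local laboratories report readings above 2+. The SAP leaves laboratory detail to protocol Section 8.2.3, which is not at hand.

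It is tempting to estimate how many women would be miscoded. The documents do not allow it. The SAP gives no rate of readings above 2+, the 240 women are a target set before enrolment ceased, only results worse than baseline count as emerging, and some women with such readings may have been hospitalised and so properly meet Grade 4. It is also tempting to conclude that every row with an event in its Grade 4 needs a cap at Grade 3. That goes too far: the other 13 event-only rows checked have no gap, and some rows define Grade 4 by a number or an event. Creatinine is Grade 4 above 2.5 mg/dL or with dialysis, and fibrinogen decrease is Grade 4 below 100 mg/dL or with gross bleeding or DIC. A general cap could wrongly downgrade those values.

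**What to change.** Reconcile Section 5.6.2 with the urine table in Appendix 6 by adding to the gap rule:

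*Urine protein or glucose results above 2+ are tabulated with the highest value-based grade (Grade 3); Grade 4 for these two parameters is assigned only when the clinical event named in the table is recorded.*

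Keep the sentence to these two parameters, so that creatinine, fibrinogen decrease and other rows with a mixed Grade 4 are unchanged. The cost is one SAP sentence and one condition in the grading program, which must read the recorded event. Data collection does not change, nor does the frequency summary of the urine categories as reported. The sentence concerns table coding only and has no bearing on patient care.

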* The laboratory values provided in the tables serve as guidelines and are dependent upon institutional normal parameters. Institutional normal reference ranges should be provided to demonstrate that they are appropriate.

** The clinical signs or symptoms associated with laboratory abnormalities might result in characterization of the laboratory abnormalities as potentially life-threatening (Grade 4). For example, a low sodium value that falls within a Grade 3 parameter (125-129 mEq/L) should be recorded as a Grade 4 hyponatremia event if the participant had a new seizure associated with the low sodium value.

***ULN is the upper limit of the normal range.

Hematology *	Mild (Grade 1)	Moderate (Grade 2)	Severe (Grade 3)	Potentially Life Threatening (Grade 4)
Hemoglobin (Female) - mg/dL	11.0 - 12.0	9.5 - 10.9	8.0 - 9.4	< 8.0
Hemoglobin (Female) change from baseline value - mg/dL	Any decrease – 1.5	1.6 - 2.0	2.1 - 5.0	> 5.0
Hemoglobin (Male) - mg/dL	12.5 - 13.5	10.5 - 12.4	8.5 - 10.4	< 8.5
Hemoglobin (Male) change from baseline value – mg/dL	Any decrease – 1.5	1.6 - 2.0	2.1 - 5.0	> 5.0
WBC Increase - cell/mm ³	10,800 - 15,000	15,001 - 20,000	20,001 - 25,000	> 25,000
WBC Decrease - cell/mm ³	2,500 - 3,500	1,500 - 2,499	1,000 - 1,499	< 1,000
Lymphocytes Decrease - cell/mm ³	750 - 1,000	500 - 749	250 - 499	< 250
Neutrophils Decrease - cell/mm ³	1,500 - 2,000	1,000 - 1,499	500 - 999	< 500
Eosinophils - cell/mm ³	650 - 1500	1501 - 5000	> 5000	Hypereosinophilic
Platelets Decreased - cell/mm ³	125,000 - 140,000	100,000 – 124,000	25,000 - 99,000	< 25,000
Prothrombin time (PT) – increase by factor	1.0 – 1.10 x ULN**	1.11 – 1.20 x ULN	1.21 – 1.25 x ULN	> 1.25 ULN
Partial thromboplastin time (PTT) – increase by factor	1.0 – 1.2 x ULN	1.21 – 1.4 x ULN	1.41 – 1.5 x ULN	> 1.5 x ULN
Fibrinogen increase - mg/dL	400 - 500	501 - 600	> 600	
Fibrinogen decrease - mg/dL	150 - 200	125 – 149	100 – 124	< 100 or associated with gross bleeding or disseminated intravascular coagulation (DIC)

* The laboratory values provided in the tables serve as guidelines and are dependent upon institutional normal parameters. Institutional normal reference ranges should be provided to demonstrate that they are appropriate.

** ULN is the upper limit of the normal range.

VAC31518 (JNJ-78436735)

Statistical Analysis Plan VAC31518COV2004 HORIZON 1

Urine *	Mild (Grade 1)	Moderate (Grade 2)	Severe (Grade 3)	Potentially Life = Threatening (Grade 4)

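### As worded, the rule that a value within local normal limits counts as normal also resets hemoglobin change-from-baseline grades, because the change row is not exempted

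*SAP*

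**What the plan says.** Section 5.6.1.2 sets the scale: "All AEs and laboratory data will be coded for severity using a modified version of the FDA grading table", which is Appendix 6 (Section 6.6). The hematology part of that appendix gives two rows for women:

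- "Hemoglobin (Female) - mg/dL": grade 1 is 11.0–12.0, grade 2 is 9.5–10.9, grade 3 is 8.0–9.4, grade 4 is below 8.0.
- "Hemoglobin (Female) change from baseline value - mg/dL": grade 1 is any decrease up to 1.5, grade 2 is 1.6–2.0, grade 3 is 2.1–5.0, grade 4 is above 5.0.

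Section 5.6.2 then lists derivation rules under the lead-in "In determining toxicity grades, the following rules are applied". The last of them concerns a value that has a grade in the FDA table, "but using the local laboratory it falls within normal limits, the value is considered as normal". The single illustration is a grade 1 result. The rule sentence names no exempt parameter or row and sets no grade ceiling. The SAP has no other rule on how the two hemoglobin rows interact.

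**The concern.** A local reference range describes absolute concentrations. It does not say whether a given fall within one participant is unremarkable. If the rule is programmed as written, a test on the absolute value decides whether a grade based on change survives. A fall that the appendix calls grade 3 is then tabulated as no abnormality because the end value is still inside the site's range.

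At stake is the worst-grade table of emerging laboratory abnormalities. Section 5.6.2 plans hemoglobin sampling through Day 29, at delivery and 42 days after delivery, and Appendix 8 lists vaginal and postpartum hemorrhage among the pregnancy-related events, so falls in hemoglobin are relevant here. Section 5.6.2 describes continuous laboratory summaries but no summary of change from baseline. Within the SAP text, the change row is therefore the only stated measure of how far an individual participant has fallen.

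**Working it through.** There is no plan figure to reproduce, since no sample size or error rate depends on this rule. The check applies the rule to the printed bands.

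**Inputs.** The bands are those of Appendix 6, taken as printed. The SAP does not give the local lower limit of normal (LLN). I assume 10.5 to 12.0 on the same scale. Where both rows give a grade, I take the higher, because the SAP does not say how to combine them.

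**Condition.** A fall of size d ends within local limits when baseline − d ≥ LLN, that is, when baseline ≥ LLN + d (assuming the end value is not above the upper limit). The smallest grade 3 fall is d = 2.1:

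- LLN 10.5: 10.5 + 2.1 = 12.6
- LLN 11.0: 11.0 + 2.1 = 13.1
- LLN 11.5: 11.5 + 2.1 = 13.6
- LLN 12.0: 12.0 + 2.1 = 14.1

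For the smallest grade 2 fall (d = 1.6) the thresholds run from 10.5 + 1.6 = 12.1 to 12.0 + 1.6 = 13.6. For the smallest grade 4 fall at one decimal (d = 5.1) they run from 15.6 to 17.1.

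**Examples.**

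| Baseline to end value | Fall | Change row | Absolute row | Result under the rule as written | Result if the rule covers absolute grades only |
|---|---|---|---|---|---|
| 14.5 to 12.2 | 2.3 | Grade 3 | none (above 12.0) | Normal for every LLN from 10.5 to 12.0 | Grade 3 |
| 13.5 to 11.4 | 2.1 | Grade 3 | Grade 1 | Normal for LLN 10.5 or 11.0; grade 3 for LLN 11.5 or 12.0 | Grade 3 |
| 13.0 to 10.9 | 2.1 | Grade 3 | Grade 2 | Normal for LLN 10.5; grade 3 for LLN 11.0, 11.5 or 12.0 | Grade 3 |

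The first line shows the main loss: the absolute row has nothing to report, and the rule removes the only grade there is. The second and third lines show that the change row keeps some effect, because it still lifts a grade 1 or 2 result to grade 3 once the value is outside local limits.

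**The case against.** The strongest reply is that the rule was never meant to reach the change row. It speaks of a value that the local laboratory finds within its limits. A laboratory flags a concentration, whereas a fall from baseline is a derived quantity with no local limits. The only illustration, "then the value can indeed be considered normal even when according to the FDA table it would be 'Grade 1", also points to borderline absolute results. This reading is plausible, but it is not written. The lead-in covers all toxicity grading and the rule sentence is unrestricted, so two programmers could produce different tables.

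Several further points stand. The appendix footnotes say the grades are guidelines that depend on institutional ranges, so some dependence on site is a declared principle for every graded parameter and not a fault peculiar to hemoglobin. Hemoglobin values still enter the continuous summaries, and a fall reported as an adverse event is still tabulated or listed. The study is descriptive, with no formal hypothesis, and output details may be refined in a data presentation document that is not at hand.

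A reader might infer that the rule makes the change row redundant, or that large falls disappear from the safety data. The documents support neither. The row still raises grades outside local limits, and only the grade tables are affected. Nor does the SAP say what the change row is for, so the point cannot rest on a stated purpose that the rule defeats.

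**Conclusion.** The concern holds in a limited form. On its plain wording the rule in Section 5.6.2 resets to normal a grade 2, 3 or 4 hemoglobin fall that ends within the local range. For the smallest grade 3 fall this needs a baseline of at least the local lower limit plus 2.1, which is 12.6 to 14.1 under assumed limits of 10.5 to 12.0. Larger falls need correspondingly higher baselines. The effect is confined to the toxicity-grade tables. How many participants are affected cannot be computed, because the SAP gives neither local ranges nor a hemoglobin distribution. It is worth correcting because the literal rule yields a wrong grade and the correction is cheap, but no main conclusion of the study is shown to depend on it.

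**What to change.** Add one sentence to the bullet in Section 5.6.2: *This rule applies only to grades based on absolute values; grades based on change from baseline (hemoglobin) are assigned regardless of the local normal range.* With that, every fall of 2.1–5.0 keeps grade 3 and every fall above 5.0 keeps grade 4 at all sites.

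The cost is one sentence and a small programming change, with no new data. The drawback is that the change row grades any decrease up to 1.5 as grade 1, so more grade 1 entries will appear. Showing the change-based grades as their own parameter keeps them apart from the absolute grades. That is a display choice; the sentence on scope is the necessary part.

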5.6.3. Other Obstetric Assessments

Obstetric medical history findings at baseline will be summarized and listed.

Delivery history findings at birth will be summarized and listed.

For further details on both assessments refer to CTP 8.2.4.

5.6.4. Other Neonatal Assessments

Neonatal medical history findings at birth will be summarized and listed.

Neurodevelopmental status will be measured using the Ages & Stages Questionnaire, 3rd edition (ASQ-3; Schonhaut 2013). The ASQ-3 includes a series of questions designed to assess 5 areas of development (communication, gross motor, fine motor, problem solving and personal-social). Individual development scores are then classified into "white", "gray" or "black" zones using predefined cut-off values (with "white" the highest score and "black" the lowest score). Findings as captured in the eCRF (scores classified by color-codes and if pediatrician contact was advised) will be summarized by timepoint and listed.

For further details on both assessments refer to CTP 8.2.5.

